Appendix 4 (cont'd)
DAID Toxicity Grading Tables for Laboratory Abnormalities

CHEMISTRIES				
	Grade 1	Grade 2	Grade 3	Grade 4
Hyponatremia	130–135 mEq/L	123–129 mEq/L	116–122 mEq/L	< 116 mEq/L or abnormal sodium with mental status changes or seizures
Hypernatremia	146–150 mEq/L	151–157 mEq/L	158–165 mEq/L	> 165 mEq/L or abnormal sodium with mental status changes or seizures
Hypokalemia	3.0–3.4 mEq/L	2.5–2.9 mEq/L	2.0–2.4 mEq/L or intensive replacement therapy or hospitalization required	< 2.0 mEq/L or abnormal potassium with paresis ileus or life-threatening arrhythmia
Hyperkalemia	5.6–6.0 mEq/L	6.1–6.5 mEq/L	6.6–7.0 mEq/L	> 7.0 mEq/L or abnormal potassium with life-threatening arrhythmia
Hypoglycemia	55–64 mg/dL	40–54 mg/dL	30–39 mg/dL	< 30 mg/dL or abnormal glucose with mental status changes or coma
Hyperglycemia (nonfasting and no prior diabetes)	116–160 mg/dL	161–250 mg/dL	251–500 mg/dL	> 500 mg/dL or abnormal glucose with ketoacidosis or seizures
Hypocalcemia (corrected for albumin)	8.4–7.8 mg/dL	7.7–7.0 mg/dL	6.9–6.1 mg/dL	< 6.1 mg/dL or abnormal calcium with life threatening arrhythmia or tetany
Hypercalcemia (corrected for albumin)	10.6–11.5 mg/dL	11.6–12.5 mg/dL	12.6–13.5 mg/dL	> 13.5 mg/dL or abnormal calcium with life-threatening arrhythmia
Hypomagnesemia	1.4–1.2 mEq/L	1.1–0.9 mEq/L	0.8–0.6 mEq/L	< 0.6 mEq/L or abnormal magnesium with life-threatening arrhythmia

Appendix 4 (cont'd)

DAID Toxicity Grading Tables for Laboratory Abnormalities

CHEMISTRIES				
	Grade 1	Grade 2	Grade 3	Grade 4
Hyperbilirubinemia (when accompanied by any increase in other liver function test)	1.1– < 1.25 × ULN	1.25– < 1.5 × ULN	1.5–1.75 × ULN	> 1.75 × ULN
Hyperbilirubinemia (when other liver function are in the normal range)	1.1– < 1.5 × ULN	1.5– < 2.0 × ULN	2.0–3.0 × ULN	> 3.0 × ULN

dL = deciliter; L = liter; mEq = milliequivalent; mg = milligram; ULN = upper limit of normal.

ENZYMES				
	Grade 1	Grade 2	Grade 3	Grade 4
AST (SGOT)	1.1– < 2.0 × ULN	2.0– < 3.0 × ULN	3.0–8.0 × ULN	> 8.0 × ULN
ALT (SGPT)	1.1– < 2.0 × ULN	2.0– < 3.0 × ULN	3.0–8.0 × ULN	> 8.0 × ULN
GGT	1.1– < 2.0 × ULN	2.0– < 3.0 × ULN	3.0–8.0 × ULN	> 8.0 × ULN
Alkaline Phosphatase	1.1– < 2.0 × ULN	2.0– < 3.0 × ULN	3.0–8.0 × ULN	> 8.0 × ULN
Amylase	1.1–1.5 × ULN	1.6–2.0 × ULN	2.1–5.0 × ULN	> 5.1 × ULN
Lipase	1.1–1.5 × ULN	1.6–2.0 × ULN	2.1–5.0 × ULN	> 5.1 × ULN
*CPK – mg/dL	1.25–1.5 × ULN	1.6–3.0 × ULN	3.1–10.0 × ULN	> 10 × ULN

ALT = alanine transaminase; AST = aspartase transaminase; CPK = creatine phosphokinase; dl = deciliter; GGT = Gamma-glutamyl transferase; mg = milligram; SGOT = serum glutamic oxaloacetic transaminase; SGPT = serum glutamic pyruvic transaminase; ULN = upper limit of normal.

URINALYSIS				
	Grade 1	Grade 2	Grade 3	Grade 4
Proteinuria	1+ or 200 mg–1 g loss/day	2–3+ or 1–2 g loss/day	4+ or 2–3.5 g loss/day	Nephrotic syndrome or > 3.5 g loss/day
Hematuria	Microscopic only < 10 RBC/hpf	Gross, no clots > 10 RBC/hpf	Gross, with or without clots, OR red blood casts	Obstructive or required transfusion
*Glucose	Trace	1+	2+	Hospitalization for hyperglycemia

g = gram; hpf = high power field; mg = milligram; RBC = red blood cell.

Appendix 5

Anaphylaxis Precautions and Management

Administration of MHAA4549A will be performed in a setting with emergency medical equipment and personnel who are trained to monitor for and respond to medical emergencies. A qualified physician *or medically qualified designee* will be on site during study drug administration for all patients.

The following equipment is needed in the event of a suspected anaphylactic reaction during study drug infusion:

- Airway management equipment
- O₂
- Epinephrine for subcutaneous, intravenous, and/or endotracheal use in accordance with standard practice
- Antihistamines
- Corticosteroids
- IV infusion solutions, tubing, catheters, and tape

The following are the procedures to follow in the event of a suspected anaphylactic reaction during study drug infusion:

- Stop the study drug infusion.
- Maintain an adequate airway.
- Administer antihistamines, epinephrine, or other medications as required by patient status and directed by the physician in charge.
- Continue to observe the patient and document observations.

Appendix 6 Adult Patient Symptom Diary

This diary will keep track of your flu symptoms and temperature during the study. You should complete it 2 times a day: when you first wake up in the morning (before getting out of bed) and about 12 hours later. Remember to take your temperature before you take any medicines to help your flu symptoms.

Please rate each symptom based on how you feel right now.

Symptom	None 0	Mild 1	Moderate 2	Severe 3
1. Nasal Congestion				
2. Sore Throat				
3. Cough				
4. Aches and Pains				
5. Fatigue (tiredness)				
6. Headache				
7. Chills/sweats (feverish)				

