3.4.2 Secondary Outcome Measures

- Time to alleviation of all symptoms (nasal congestion, sore throat, cough, aches, fatigue, headaches, chills/sweats) with resolution maintained for 24 hours (without use of symptom relief medications) as defined by a rating 0 (none) or 1 (mild) for each symptom on a 4-point scale of 0–3. For patients who enroll with mild symptoms, the symptom score must be reduced by 1 point during the study duration.
- Incidence of reinfection or relapse with influenza at 100 days after end of treatment
- Incidence of hospitalization for influenza-related complications at 100 days after end of treatment and length of stay
- Antibiotic usage for secondary bacterial respiratory infections
- Incidence of complications of influenza (e.g., pneumonia, exacerbations of chronic lung disease, myocarditis, acute respiratory distress syndrome (ARDS), otitis media, or other influenza related complications)
- *Incidence of death*

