4.5.9 Patient Daily Symptom Diary

Patients will use paper diaries to record symptom data ([Nicholson et al. 2000](#); [Treanor et al. 2000](#)) ([Appendix 6](#)). The investigator staff will provide the paper diary and instructions for completing the symptom diary. The purpose of the diary is to record

any symptoms of influenza-like illness, symptom relief medications and temperature (*oral*). The symptom diary card, symptom relief medications and temperature should be completed two times daily: when a patient first wakes up in the morning (before getting out of bed) and ~12 hours later up to Day 14 or until resolution of symptoms (defined as a total symptom score of 0–1 for 24 hours without use of symptom relief medications). Temperature should be taken before administration of acetaminophen/paracetamol and/or NSAIDs (see Section 4.4.1 for permitted medications). Patients should be encouraged to stay consistent with the diary schedule and sites should check that patients are able to take their temperature properly. Day 1 entry will be completed within 6 hours prior to start of study infusion.

Data from paper diaries will be entered into the EDC system by site staff.

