6.5 SECONDARY EFFICACY ANALYSES

The efficacy analyses will include all randomized patients who are confirmed to be influenza A infected, with patients grouped according to the treatment assigned at randomization. Efficacy parameters to be evaluated include duration and severity of influenza symptoms, hospitalization, and influenza-related complications.

Time to event data will be analyzed using Kaplan-Meier methodology and will be summarized using n, median when estimable, hazard ratios, and 95% confidence intervals. Patients who are lost to follow-up (while event free) will be censored at the time that they are last known to be event free.

Estimation of the treatment difference of proportions and its 95% confidence interval will be calculated using stratum-adjusted Mantel-Haenszel methodology ([Koch et al. 1989](#)). For continuous endpoints, Analysis of Covariance methods (after appropriate transformation of data) will be used to estimate treatment differences and 95% confidence intervals.

Other than censoring in the time to event analyses, no other imputation for missing data will be performed.

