Appendix 6 (cont'd) **Adult Patient Symptom Diary**

Temperature:

Please take your temperature now.

What is your temperature right now? (Measure before taking fever medication): _____

(Choose °C or °F)

Did you measure a temperature >38.0°C (100.4°F) in the past 12 hours?

____ Yes

____ No

What was the time and temperature?: _____

Medications for relief:

Please look at your “allowed medication” wallet card. It shows the most common names of these medications (i.e., acetaminophen/paracetamol, ibuprofen, other NSAIDs)

Have you taken any of these “allowed medications” to help your flu symptoms in the past 12 hours?

____ Yes

____ No

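### The diary's before-medicine instruction covers temperature but not the seven symptom ratings, so some severity ratings may be made after a dose

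*Combined protocol and SAP*

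**What the plan says.** Appendix 6 gives the entry schedule: "You should complete it 2 times a day: when you first wake up in the morning (before getting out of bed) and about 12 hours" (counted from the first entry). The seven symptoms come first on the form, each scored 0 to 3, under the instruction "Please rate each symptom based on how you feel right now". Temperature follows, and then a yes/no question on whether an allowed medicine was taken "to help your flu symptoms in the past 12 hours".

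The order of measurement and medicine is fixed for temperature only. Appendix 6 says "Remember to take your temperature before you take any medicines to help your flu symptoms". Section 4.5.9 says "Temperature should be taken before administration of acetaminophen/paracetamol and/or NSAIDs (see Section 4.4.1 for permitted medications". The diary footnotes of Appendices 1 and 2 repeat the rule, again for temperature alone.

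The ratings are used in two places:

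- **Time to alleviation (Section 3.4.2).** Every symptom must reach 0 or 1 and stay there for 24 hours with no relief medicine. A further rule reads "For patients who enroll with mild symptoms, the symptom score must be reduced by 1 point during the study duration".
- **Severity.** Section 2.2 lists it as a secondary objective, and Section 6.5 says "Efficacy parameters to be evaluated include duration and severity of influenza symptoms". Neither place attaches a condition about relief medicine.

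Section 4.4.1 permits acetaminophen/paracetamol and NSAIDs for severe symptoms and requires their use to be recorded in the diary.

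**The concern.** Temperature is not part of the alleviation endpoint in Section 3.4.2; the seven symptoms are. Yet the written safeguard against measuring under the effect of a medicine covers temperature and leaves the symptoms out. A rating made shortly after a dose can understate a symptom, and nothing in the instructions discourages it.

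Two uses of the data are exposed. The first is severity. Section 4.4.1 ties relief medicine to severe symptoms, so if one arm has more severe illness it may also have more post-dose ratings, which would narrow the observed difference between arms. The second is the Day 1 entry. If it decides who enrolled with mild symptoms, a rating lowered by medicine changes what that patient must later achieve.

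**Working it through.** The plan states no figure that depends on the diary. Its design figures (141 enrolled for 120 evaluable, and the adverse-event probabilities in Table 5) concern dropout and safety. The check is therefore a reading of the texts side by side, with two small calculations.

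**1. Which safeguard applies to which item**

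| Item | Before-medicine rule | 12-hour look-back |
|---|---|---|
| Temperature | Yes (Section 4.5.9; Appendices 1, 2 and 6) | Yes: "Did you measure a temperature >38.0°C (100.4°F) in the past 12 hours" |
| Relief medicine | Not applicable | Yes (yes/no) |
| Seven symptom ratings | None stated | None |

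The gap in the before-medicine column is real and is the same everywhere the rule appears.

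**2. Does it reach the alleviation event?** Entries are 12 hours apart, so a 24-hour period touches 24/12 + 1 = 3 ratings and is covered by 24/12 = 2 medicine questions. Two consecutive answers of No therefore cover the whole 24 hours. A low rating obtained under medicine does not count toward alleviation, provided the condition is applied as written.

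**3. Does it reach severity?** The readable parts of Sections 3.4.2, 6.5 and 6.5.1 give no rule for ratings made under medicine, so such ratings enter a severity comparison unmarked. The medicine question, as it appears in the diary text, asks for no time of intake. A Yes shows that a dose fell in the preceding 12 hours, but not whether it came shortly before the rating.

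**4. Does it reach baseline?** Section 6.3 takes the last value before study drug as baseline. Section 4.5.9 places the Day 1 entry within 6 hours before the infusion, so that entry is not reliably a waking one. Suppose the mild-symptom rule is applied to each symptom from the Day 1 rating, which Section 3.4.2 does not say:

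- Symptom rated 2 without medicine: it must reach 0 or 1, a fall of at least 1 point, to a target of 1.
- Same symptom rated 1 after a dose: it must fall by 1 point, and 1 - 1 = 0, so the target is 0.

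The target moves by one point for that symptom. Any such dose precedes the infusion, so randomisation balances the effect across arms in expectation. It adds noise and does not systematically favour an arm.

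**5. How a post-dose rating can arise.** The ratings are printed before the temperature field. A patient who completes the form in one sitting and obeys the temperature rule has rated the symptoms before the next dose. Two routes remain: an entry split around a dose (temperature, then medicine, then ratings), and carry-over from an earlier dose.

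**The case against.** The strongest case against is that the form largely protects itself. The morning entry is made on waking, before getting out of bed. The ratings come first on the page, and the temperature rule in practice governs the whole sitting. Every entry records recent medicine use, so medicated entries can be found at analysis. Comparing scores with relief medicine permitted in all arms is a legitimate choice. The exploratory endpoints and analyses are blacked out and may define how severity is scored. Most of this stands. It narrows the exposure to split entries, carry-over and Day 1, but it does not supply the missing instruction.

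Three stronger readings are tempting, and the documents do not support them:

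- **Medicated symptoms are recorded as mild.** Patients record what they feel, from 0 to 3. Nothing in the text makes a medicated symptom a 1.
- **Alleviation is declared falsely under medicine.** The 24-hour medicine-free condition and the 12-hour question prevent this.
- **The symptoms need a look-back like the one for fever.** It is true that an untreated symptom returning between entries leaves no record, and that the 24-hour period rests on point ratings. But the fever item asks about a reading actually taken, whereas a symptom look-back would ask for a recalled judgement. Momentary or recalled rating is a choice of instrument on which reasonable reviewers differ, and tying a look-back to Section 3.4.2 would alter the event definition. The gap is present in every arm, and the documents do not show which way it would move the hazard ratio.

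**Conclusion.** The concern holds in a limited form. The before-medicine instruction omits the seven symptom ratings in Appendix 6, in Section 4.5.9 and in the diary footnotes of Appendices 1 and 2. The consequence is mainly that some post-dose ratings may enter the severity comparison, with some added noise at baseline if the Day 1 entry drives the mild-symptom rule. The alleviation event is protected.

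The size cannot be computed. The documents give no rate of relief-medicine use by arm, no effect of a dose on the ratings, no expected difference in severity and, in the readable text, no severity score. Any percentage would rest on assumptions alone. Narrowing of the severity difference follows only if medicine use differs between arms and ratings are often made after a dose.

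Severity is a secondary objective, the primary objective is safety, and Section 6 rules out formal hypothesis testing. Priority: CONSIDER.

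**What to change.** 1. Extend the existing reminder in Appendix 6 to the whole entry, for example: 'Rate your symptoms and take your temperature first, and only then take any flu medicine.' Make the matching change in Section 4.5.9 and in the diary footnotes of Appendices 1 and 2, and state that it includes the Day 1 entry before infusion. This fixes the order within an entry; it does not change which medicines are permitted or when they may be used.
2. The wording does not remove carry-over from earlier doses. In Section 6.5, state that entries with a Yes to the existing 12-hour medicine question will be flagged, and give a sensitivity summary of severity that takes the flag into account. Because no time of intake is asked, the flag will also catch entries made many hours after a dose, so it should support a sensitivity summary and not replace the main one.

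The cost is one reworded sentence in the diary, matching edits in the protocol and one additional summary. No diary item, visit, sample or patient is added. The momentary ratings and the event definition in Section 3.4.2 stay as they are.

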Appendix 6 (cont'd) **Adult Patient Symptom Diary**

Temperature:

Please take your temperature now.

What is your temperature right now? (Measure before taking fever medication): _____

(Choose °C or °F)

Did you measure a temperature >38.0°C (100.4°F) in the past 12 hours?

____ Yes

____ No

What was the time and temperature?: _____

Medications for relief:

Please look at your “allowed medication” wallet card. It shows the most common names of these medications (i.e., acetaminophen/paracetamol, ibuprofen, other NSAIDs)

Have you taken any of these “allowed medications” to help your flu symptoms in the past 12 hours?

____ Yes

____ No

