4.4 CONCOMITANT THERAPY AND FOOD

Concomitant therapy includes any medication (e.g., prescription drugs, over-the-counter drugs, herbal or homeopathic remedies, nutritional supplements) used by a patient from 30 days prior to screening to the study completion/discontinuation visit. All such medications should be reported to the investigator and recorded on the Concomitant Medications eCRF.

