4.4.2 Prohibited Therapy

Use of the following therapies is prohibited throughout the patient's participation in the study (from enrollment to end of study):

- Any influenza antiviral therapy (e.g., oseltamivir, zanamivir, peramivir, amantadine, rimantadine) from onset of influenza-like illness (*except for recurrent influenza as described in Section 3.1.1*)
- Investigational therapy
- Oral/inhaled corticosteroids
- Antitussives or expectorants
- Combination cold or influenza remedies
- Antihistamines
- Herbal medicines for influenza virus infection

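### Two 'No' answers to the diary's 12-hour medication question do not establish the 24 medication-free hours that time to alleviation requires

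*Combined protocol and SAP*

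**What the plan says.** **Endpoint.** Section 3.4.2 lists time to alleviation first among the secondary outcomes. Each of seven symptoms must be rated 0 or 1, "with resolution maintained for 24 hours (without use of symptom relief medications"). The term for relief medication is not defined and is not limited to permitted drugs.

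**Source of the medication data.** Section 4.4.1 requires patients to record acetaminophen/paracetamol and NSAID use in the diary. Section 9.4 says these data are captured on paper diaries.

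**Diary item.** Appendix 6 asks, Yes or No, whether any permitted drug was taken "to help your flu symptoms in the past 12 hours". The item refers to a wallet card: "It shows the most common names of these medications (i.e., acetaminophen/paracetamol, ibuprofen, other NSAIDs"). It does not ask for drug name, dose or time.

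**Entry times.** Entries are made "when you first wake up in the morning (before getting out of bed) and about 12 hours later". The diary also instructs: "Remember to take your temperature before you take any medicines to help your flu symptoms".

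**Diary stopping rule.** Section 4.5.9 allows the diary to end before Day 14 once the total symptom score is 0–1 "for 24 hours without use of symptom relief medications".

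**Other products and the second record.** Section 4.4.2 prohibits antitussives, expectorants, antihistamines and "Combination cold or influenza remedies". Section 4.4 covers all medication, over-the-counter drugs included: "All such medications should be reported to the investigator and recorded on the Concomitant Medications eCRF". Appendix 1, footnote e, asks patients to report everything taken at home. No section says whether the diary or this eCRF decides the 24-hour condition.

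**The concern.** The endpoint rule runs over 24 hours and the diary is its designated source, so two consecutive diary answers should cover those hours without a hole. They do so only if no gap between entries exceeds 12 hours. The schedule does not guarantee that, because one entry is tied to waking and the other is only approximately 12 hours later. Any hole falls immediately after an entry. That is a plausible time to take a dose, since patients are told to measure temperature first.

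The item is also narrower than the endpoint. Section 3.4.2 excludes relief medication in general, while the diary asks only about permitted drugs. A patient who takes a prohibited cough or cold product truthfully answers No.

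At stake is whether the medication-free condition can be verified. If it cannot, some alleviation times may be dated too early. Section 6.5 will report medians, hazard ratios and 95% confidence intervals for time-to-event data, which include this endpoint.

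**Working it through.** The plan states no figure that depends on the look-back, so there is nothing to reproduce. The check is one of coverage.

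**1. Inputs from the documents.** Look-back 12 h (Appendix 6); nominal entry spacing about 12 h (Appendix 6, Section 4.5.9); required medication-free period 24 h (Section 3.4.2).

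**2. Uncovered time in a 24-hour window.** For the two gaps g1 and g2 between three successive entries:

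uncovered = max(0, g1 − 12) + max(0, g2 − 12).

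- Exact spacing, 12 h and 12 h: 0 h uncovered. A dose just after an entry is still inside the next look-back.
- Constant waking time, evening entry d hours off schedule: the gaps are 12 + d and 12 − d, so |d| hours are uncovered. For d = 0.5, 1 and 3 h this gives 0.5, 1 and 3 h.
- Evening entry on time, next waking s hours late: s hours uncovered. Waking early leaves none.

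**3. Example.** Entries at 07:00 and 18:30, ibuprofen at 18:45.

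- At 07:00 the dose is 12 h 15 min old, so the truthful answer is No.
- At 18:30 the dose is 23 h 45 min old, so the answer is again No.
- The two look-backs cover 19:00–07:00 and 06:30–18:30. The hole is 18:30–19:00, and the dose lies in it.

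**4. Chance that a dose shortly after an entry escapes.** Assumption, not in the documents: gap normal with mean 12 h and standard deviation SD. For a dose taken a delay t after an entry:

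P(gap > 12 + t) = 1 − Φ(t / SD).

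| Delay t | SD 0.5 h | SD 1 h | SD 2 h |
|---|---|---|---|
| 15 min | 1 − Φ(0.50) = 31% | 1 − Φ(0.25) = 40% | 1 − Φ(0.125) = 45% |
| 30 min | 1 − Φ(1.00) = 16% | 1 − Φ(0.50) = 31% | 1 − Φ(0.25) = 40% |

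**5. Uncovered time per 24-hour window.** Simulation of 400,000 windows. Assumption: waking time and the deviation of the evening entry from 12 h after waking are independent and normal, with the same SD.

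| SD of each | Mean uncovered | Windows with more than 0.5 h uncovered |
|---|---|---|
| 0.25 h | 0.27 h | 17% |
| 0.5 h | 0.54 h | 46% |
| 1 h | 1.09 h | 67% |

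**6. What these figures are not.** Step 4 is conditional on a dose having been taken at that delay. A false alleviation event also needs every symptom at 0 or 1 at the ratings concerned, and no other dose in the window that is captured. The documents give no frequency or timing of dosing, so a false-event rate cannot be computed.

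**7. Drug scope, side by side.** Section 3.4.2 excludes relief medication without qualification. Appendix 6 asks only about permitted drugs. Section 4.4 sends everything else to the Concomitant Medications eCRF. No sentence connects that form to the endpoint.

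**The case against.** The strongest reply is that an escaped dose is, by construction, more than 12 hours old at the next entry, and symptoms are rated as felt at that moment. A reader might infer that medication is holding the scores down and creating false recoveries. The documents do not support that: nothing shows that a dose this old still affects the ratings. What is shown is that the stated rule can be breached without being detected. This part of the reply stands.

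The behaviour required is also particular. Section 4.4.1 permits these drugs for severe symptoms, and any rating of 2 or 3 inside the window blocks alleviation by itself. The patient would have to rate everything none or mild and then take a dose soon afterwards. Dosing right after an entry is an inference from the temperature instruction, not a documented pattern. This stands as a limit on frequency.

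Prohibited remedies are not lost to the trial. They belong on the Concomitant Medications eCRF, home use must be reported, and protocol deviations are summarised by arm (Section 6.2). It would also be too strong to say that this form cannot supply dose times, because its fields are not shown. What remains is the missing rule linking it to the endpoint. After Day 7, Section 3.2 schedules no contact until the Day 14 call, so for that week the form may depend on recall.

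A reader might also take the diary stopping rule to be the alleviation criterion, so that a falsely alleviated patient stops recording. It is not. Stopping needs a total score of 0–1, whereas alleviation allows each of seven symptoms to be 1, a total of up to 7. Only the medication clause is shared.

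**Conclusion.** The diary as worded cannot verify the 24-hour medication-free condition unless entries are never more than 12 hours apart, and it does not ask about all the medication that the endpoint excludes. This follows from the text without any assumption. The 31%, 40% and 45% figures rest on an assumed normal gap and a dose 15 minutes after an entry. They show that modest irregularity is enough to open the hole, not how often an event is misdated.

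The consequence is possible misclassification of time to alleviation. A reader might go on to infer bias toward no difference, on the ground that placebo patients would use more relief medication. That requires both an effective antibody and more placebo dosing in exactly these gaps, and the documents establish neither. Size and direction between arms are unknown.

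The primary objective is safety, Section 6 plans no formal hypothesis testing, and no stated sample size or probability depends on this item. It is an inexpensive improvement worth making, not a threat to the trial's main purpose.

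**What to change.** **Appendix 6.** Replace the medication item with: *Since your last diary entry, have you taken any medicine for flu, cold, cough, allergy, pain or fever symptoms? If yes: name and time of last dose.* Uncovered time then falls to 0 h for any spacing, provided no entry is missed, and the time of last dose lets the 24-hour rule be checked directly. Reword the fever item to the same look-back; it already asks for a time. Asking about prohibited products does not alter their status under Section 4.4.2.

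**Section 3.4.2.** State that any relief medication, permitted or prohibited, recorded in the diary or on the Concomitant Medications eCRF within the 24-hour window means that the alleviation criterion is not met. Add a convention for eCRF records that carry a date but no time.

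**Cost.** A reprinted paper diary (Version 2 already revised it), two extra eCRF fields, one edited endpoint definition, and slightly more writing for patients and data entry for sites. No additional visits or patients.
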